2.5 Analysis of the primary objective

All patients in the Full Analysis Set (FAS) will be included in the primary analysis.

In the event that the study is stopped early for efficacy at the second interim analysis, or the study is terminated early by the sponsor due to prolonged COVID-19 impact, the main, supportive and subgroup analyses for the primary endpoint described in this section will be performed using the same analysis cut-off date as the second interim analysis to include data prior to 01-Mar-2020.

If the study is not stopped at the second interim analysis and continues to the end, the main, supportive and subgroup analyses for the primary endpoint described in this section will be performed as planned using all data accrued up to the end-of-study analysis cut-off (31-Dec-2020).

See Section 2.5.4 for sensitivity and supplementary analyses for the primary endpoint, including those added for the COVID-19 impact.

2.5.1 Primary endpoint

The primary efficacy variable is time to first occurrence of a confirmed composite endpoint of cardiovascular death, HF hospitalization or outpatient HF. The confirmation of the primary composite events will be based on an adjudication process by an independent CEC.

Note that deaths which cannot be classified by the adjudication committee as CV or non-CV death (for example due to lack of information), will be counted as a CV death for the purpose

of the primary endpoint. Unless otherwise specified, this is applicable to all efficacy endpoints with a CV death component.

Time-to-event is computed as the number of days from randomization to the date of the primary endpoint event (first occurrence). A patient without an event will be censored at the last date the endpoint status was completely known* or at the time of death from non-CV causes (i.e. any death which is confirmed to be a non-CV death by the CEC).

* This date could include the date of withdrawal of informed consent, date of the patient's last visit prior to the cut-off date of the analysis (whichever occurred first).

2.5.2 Statistical hypothesis, model, and method of analysis

The following null hypothesis versus the alternative will be tested at the 1-sided 2.5% type I error rate.

$H_0 : \lambda_2/\lambda_1 \geq 1$ (i.e., the hazard rate of the first confirmed primary event in the LCZ696 group (λ_2) is greater than or equal to the hazard rate in the ramipril group (λ_1)) *versus*

$H_1 : \lambda_2/\lambda_1 < 1$ (i.e. the hazard rate of the first confirmed primary event in the LCZ696 group (λ_2) is less than the hazard rate in the ramipril group (λ_1))

λ_2/λ_1 is called the hazard ratio of LCZ696 relative to ramipril.

The time-to-first confirmed primary endpoint will be analyzed using a Cox proportional hazards model stratified by STEMI/NSTEMI, with treatment, PCI use at baseline and region included as factors in the model. This model allows the hazard rates to vary with time while the hazard ratio is assumed to be constant, i.e., independent of time, within each stratum. The hazard ratio for LCZ696 vs. ramipril, the associated 2-sided 95% confidence interval and the 1-sided and 2-sided p-values will be presented from the analysis.

The Kaplan-Meier estimates of the cumulative event rate (1-survival function) for each treatment (and strata) will be tabulated and will also be presented graphically.

2.5.3 Handling of missing values/censoring/discontinuations

In general, for a time-to-first event endpoint, the censoring date for a non-fatal endpoint or an endpoint with non-fatal event as a component (even if fatal event is also another component) is defined as one of the following (whichever occurred first):

- Date when the patient withdrew informed consent
- Date of the patient's last visit (including telephone visit)
- Date of death
- Analysis cut-off date¹

The censoring date for a fatal endpoint (time-to-first event) is defined as one of the following (whichever occurred first):

- Date when the patient withdrew informed consent
- Patient's last known alive date
- Date of death
- Analysis cut-off date¹

¹ Analysis cut-off date will be 31-Dec-2020 for the primary/main analyses, and 29-Feb-2020 for analyses using pre-COVID impact data prior to 1-Mar-2020.

Note that every effort will be made to follow all patients until the end of the study, regardless of adherence to study treatment. The analysis methods specified are valid under the assumption that the censoring mechanism is independent of the event generating process (non-informative censoring).

Missing or partially missing event dates will be imputed according to the rules specified in Section 5.1.3.

The censoring date for the primary endpoint will be derived using the non-fatal endpoint censoring method as described above in this section, with the censoring component date of death being that of non-CV death.

The censoring date for the components of the primary endpoint will be derived using the same principle for fatal/non-fatal endpoint as described above in this section:

- Time-to-first event of HF hospitalization (using censoring method for non-fatal endpoint)
- Time-to-first event of outpatient HF (using censoring method for non-fatal endpoint)
- Time to CV death (using censoring method for fatal endpoint)

2.5.4 Supportive analysis and sensitivity/supplementary analysis

Supportive analysis

The composition of the first confirmed composite primary efficacy endpoint will be summarized by treatment group descriptively. The time to reach the first of each individual component will be analyzed using the same methodology as the described for the primary endpoint. Note that for the components CV death and HF hospitalization, all events observed will be included in the individual component analyses and not just those which were counted as a 'first event' in the primary composite endpoint. In addition to the standard censoring mechanism described in [Section 2.5.3](#), for the analysis of time to outpatient HF, patients will be censored at the time of HF hospitalization or CV death. For the analysis of time to first HF hospitalization, patients will be censored at the time of CV death.

As supportive analyses, the following alternative definitions of the primary endpoint will be used with the primary analysis model described in Section 2.5.2:

- (a) Time to first occurrence of an investigator-reported composite endpoint of CV death, HF hospitalization or outpatient HF (with and without the analysis cut-off date of 31-Dec-2020);
- (b) Time to first occurrence of a confirmed composite endpoint of all-cause death, HF hospitalization or outpatient HF;
- (c) Time to first occurrence of a confirmed composite endpoint of CV death (including only deaths from CV causes, unknown or missing cause of deaths are not included as events), HF hospitalization or outpatient HF.

Above (a) is the investigator-reported version of the primary endpoint. (b) is the alternative definition of the primary endpoint by replacing the CV death component with all-cause death.

(c) differs from the primary endpoint in that the CV death is defined as death from CV causes only, while the primary endpoint includes CV death from unknown causes. For (c), the component analysis of CV death will also include deaths from CV causes only, and unknown or missing cause of deaths will not be considered as events.

An ‘on-treatment’ analysis ([Section 2.1.1](#)) will also be performed for the primary endpoint whereby events that occurred more than 28 days after permanent study treatment discontinuation will be excluded from the analysis. For patients without events before or at 28 days after treatment withdrawal, the censoring date will be the minimum of the date of permanent study treatment discontinuation + 28 days and the date of standard censoring for the endpoint.

The primary analysis will also be repeated for per-protocol set (PPS) for assessing robustness of results to significant protocol deviations leading to exclusion from FAS.

Sensitivity and supplementary analyses

1. If the study is stopped early for efficacy at the second interim analysis, or the study is terminated early by the sponsor due to prolonged COVID-19 impact, the following sensitivity and supplementary analyses will be performed:
 - (1) As a sensitivity analysis to the above proportional hazards analysis, treatment groups will be compared for the primary efficacy variable using a stratified log-rank test with STEMI/NSTEMI as a stratification factor, including CEC-confirmed primary endpoint events that occurred prior to 01-Mar-2020 (estimated start of COVID-19 impact globally).
 - (2) Analysis with adjustment of country instead of region in the primary analysis model as specified in [Section 2.5.2](#), using CEC-confirmed primary endpoint events that occurred prior to 01-Mar-2020.
 - (3) A supplementary analysis using the primary analysis model as specified in [Section 2.5.2](#), including all CEC-confirmed primary endpoint data accrued up to the end-of-study analysis cut-off.

2. If the study is not stopped at the second interim analysis and continues to the end, the following sensitivity and supplementary analyses will be performed:
 - (1) As a sensitivity analysis to the above proportional hazards analysis, treatment groups will be compared for the primary efficacy variable using a stratified log-rank test with STEMI/NSTEMI as a stratification factor, including all CEC-confirmed primary endpoint data accrued up to the end-of-study analysis cut-off.
 - (2) Hypothetical estimand approach (see Table 2-4 for the definition of the hypothetical estimand in a world without the COVID-19):

The estimand targeted in the original study protocol is defined in Table 2-3. In comparison, in a hypothetical world without COVID-19, the new intercurrent event due to COVID-19 is the onset of COVID-19 pandemic impact on study (see Table 2-4), which can be derived by a fixed global COVID-19 impact start date (01-Mar-

2020) or subject-specific impact start date based on information from the COVID CRF pages. A hypothetical strategy (see below methods i and ii) will be used for this new intercurrent event.

The analyses targeting this estimand will be performed with the following censoring methods:

- i. Endpoint data will be censored on 29-Feb-2020 if the patient has not experienced the endpoint by this time

This analysis will be performed using the primary analysis model as specified in [Section 2.5.2](#).

- ii. Endpoint data will be censored at the time of subject-specific COVID-19 impact start date, derived as the earliest date of the following for each patient based on the COVID-19 eCRF: (a1) study treatment discontinuation due to COVID-19; (a2) start of treatment interruption for > 3 months due to COVID-19; (b) first missed visit due to COVID-19; (c) first endpoint event impacted by COVID-19; (d) symptom onset of the first occurrence of a condition for which the patient felt the need to go to an outpatient clinic, urgent care, emergency department, or hospital but chose not to due to COVID-19.

This analysis will be performed using inverse probability of censoring weighted (IPCW) Cox proportional hazards model (Robins and Finkelstein 2000) as described in Section 2.6.5. IPCW is used to account for potential informative censoring using the subject-specific censoring method.

Table 2-3 Estimand in the original protocol :

Intercurrent event	Strategy
Permanent treatment discontinuation	Treatment policy strategy
Non-CV death	Hypothetical strategy

Primary scientific question of interest / Estimand:
 
What would be the relative risk reduction (HR) for Entresto vs Ramipril (regardless of treatment discontinuation) in patients with LV systolic dysfunction and/or pulmonary congestion following an AMI, in the composite primary endpoint, as measured by the time to first composite of CV death, HFH and outpatient HF, in the absence of death from non-CV related causes?
	

Table 2-4 Estimand in a world without the COVID-19 pandemic:

Intercurrent event	Strategy
Permanent treatment discontinuation	Treatment policy strategy

Non-CV death	Hypothetical strategy
Onset of COVID-19 pandemic impact on study	Hypothetical strategy

Primary scientific question of interest / Estimand:
 
What would be the relative risk reduction (HR) for Entresto vs Ramipril (regardless of treatment discontinuation) in patients with LV systolic dysfunction and/or pulmonary congestion following an AMI, in the composite primary endpoint, as measured by the time to first composite of CV death, HFH and outpatient HF, in the absence of COVID-19 pandemic and death from non-CV related causes?
	

Since the study was designed without a COVID-19 pandemic in mind, both the analysis targeting the estimand “in a world without COVID-19 pandemic” and the primary analysis based on all data up to the end-of-study analysis cut-off may be interpreted as addressing the estimand in the original study protocol, acknowledging that the treatment effect estimate based on the latter might be affected by the pandemic.

(3) Bayesian analysis with robust prior

Let us denote by $y_{pre} = \log(\widehat{HR}_{pre})$ the observed log(hazard ratio) based on data obtained **before** the global outbreak of COVID-19, and by $y_{post} = \log(\widehat{HR}_{post})$ the observed log(hazard ratio) based on data obtained **after** the outbreak. The true underlying log(hazard ratio) is denoted by θ . We use the normal approximation for the log(hazard ratio), and thus, when denoting the number of events by n_{pre} , n_{post} , we obtain for the likelihood

$$y_{pre} | \theta \sim N\left(\theta, \frac{4}{n_{pre}}\right)$$

$$y_{post} | \theta \sim N\left(\theta, \frac{4}{n_{post}}\right)$$

Our goal is to leverage the information obtained after the outbreak to inform the hazard ratio from the data obtained before the outbreak. However, since the impact of COVID-19 on the endpoint is unclear, we aim doing so in a robust way. Therefore, we build a prior for θ that fulfills the following two requirements:

- In case of similarity of y_{pre} and y_{post} , the information obtained after the outbreak is, to a substantial extent, taken into account
- In case of a conflict between y_{pre} and y_{post} , the information obtained after the outbreak is down-weighted in a dynamic way

These requirements can be addressed using a robust mixture prior (see e.g. Schmidli et al, 2014) consisting of two components:

Component 1: Informative prior distribution $p_{inf}(\theta) = N(y_{post}, \frac{4}{n_{post}})$, which is the posterior distribution of θ given y_{post} , when starting with an improper prior for θ

Component 2: Vague prior distribution $p_{vague}(\theta) = N(y_{post}, 2^2)$, which is a vague (unit-information) prior distribution for θ

The robust mixture prior is obtained by mixing these distributions with weights w and $1 - w$, respectively:

$$p(\theta) = w * p_{inf}(\theta) + (1 - w) * p_{vague}(\theta)$$

Finally, we obtain the posterior distribution $p(\theta|y_{pre})$ through standard Bayesian updating. As a fact of mixture calculus, the posterior is a mixture of the component-wise posteriors, but with updated weights:

$$p(\theta|y_{pre}) = \tilde{w} \times p_{inf}(\theta|y_{pre}) + (1 - \tilde{w}) \times p_{vague}(\theta|y_{pre})$$

where $p_x(\theta|y_{pre})$ is the posterior distribution of θ given data y_{pre} and prior $x \in \{inf, vague\}$.

The weights are updated according to the following rule:

$$\tilde{w} = \frac{w * m}{w * m + (1 - w) * m'}$$

$$m = \int p(y_{pre}|\theta)p_{inf}(\theta)d\theta$$

$$m' = \int p(y_{pre}|\theta)p_{vague}(\theta)d\theta$$

Finally, the weights chosen for the analysis are $w = 1 - w = 0.5$, i.e. we a priori assume there is an equal chance of similarity and conflict between y_{pre} and y_{post} . This choice is common practice in applications (Dominguez et al, 2017). The point estimate and 95% probability interval will be obtained from this posterior distribution as the median and 2.5th and 97.5th percentile, respectively. Furthermore, the posterior probability that the hazard ratio is favoring LCZ696 (i.e., $HR < 1$), will be provided. SAS code for this analysis can be found in Appendix 5.4.

- (4) Analysis of all CEC-confirmed primary endpoint data accrued up to the end-of-study analysis cut-off, using a Cox model with a “during-COVID” indicator and its interaction with treatment as time-varying covariates.

Consider the following model:

$$h(t) = h_0(t)\exp(\beta_1 \times trt + \beta_2 \times \mathbb{I}\{C(t)\} + \beta_3 \times \mathbb{I}\{C(t)\} \times trt),$$

where $\mathbb{I}\{C(t)\}$ is an indicator of “during-COVID” at patient-time t . $\mathbb{I}\{C(t)\}$ is equal to 1 if the patient-time t falls in the COVID-19 impacted period (on or after 1-Mar-2020), and is equal to 0 otherwise.

This analysis model will allow the assessment of the treatment effect in non-COVID impacted periods (before and after the COVID-impacted period, estimated by β_1). It will also allow to quantify the change in event rate during the COVID-impacted period (β_2) and the change of the treatment effect during the COVID-impacted period (β_3), however the number of events and hence precision may be low. In addition to including treatment, “during-COVID” indicator, treatment by “during-COVID” indicator interaction as covariates, this model will also adjust for region and PCI use at baseline, and be stratified by type of MI (STEMI/NSTEMI).

- (5) Weibull regression model stratified by type of MI (STEMI/NSTEMI), with treatment, PCI use at baseline and region included as factors in the model, including all CEC-confirmed primary endpoint events that occurred prior to 01-Mar-2020. Parametric model may be more powerful than the semiparametric primary model.
- (6) Analysis with adjustment of country instead of region in the primary analysis model as specified in [Section 2.5.2](#), both using all CEC-confirmed primary endpoint data accrued up to the end-of-study analysis cut-off and event data with onset date prior to 01-Mar-2020. This may recover some of the lost power by accounting for the heterogeneity of the COVID-19 impact and also the standard of care among countries within regions)

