5.3 Treatment assignment and randomization

At Visit 101 all eligible patients will be randomized via Interactive Response Technology (IRT) to one of the treatment arms. The investigator or his/her delegate will contact the IRT after confirming that the patient fulfills all the inclusion/exclusion criteria. The IRT will assign a randomization number to the patient, which will be used to link the patient to a treatment arm and will specify a unique medication number for the first package of study drug to be dispensed to the patient. The randomization number will not be communicated to the caller.

The randomization numbers will be generated using the following procedure to ensure that treatment assignment is unbiased and concealed from patients and investigator staff. A patient randomization list will be produced by the IRT provider using a validated system that automates the random assignment of patient numbers to randomization numbers. These randomization numbers are linked to the different treatment arms, which in turn are linked to medication numbers. A separate medication list will be produced by or under the responsibility of Novartis Drug Supply Management using a validated system that automates the random assignment of medication numbers to packs containing the investigational drug(s).

Randomization will be stratified by region and type of index MI (STEMI or NSTEMI).

The randomization scheme for patients will be reviewed and approved by a member of the Novartis Randomization Group.

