2.1 Data analysis general information

Data will be analyzed by Novartis Biostatistics and Statistical Reporting department according to the statistical analysis section 9.1 of the study protocol using SAS 9.4, unless otherwise specified. Further details on planned statistical analyses and data-driven regression diagnostics will be presented in the following section and in CSR Appendix 16.1.9. The same analysis plan will also be used for planned interim efficacy analyses, as applicable.

In general, the continuous variables will be summarized descriptively by presenting n, mean, SD, median, quartiles, minimum and maximum while categorical variables will be summarized by presenting count and percentage of patients in each category. Graphical presentation of summary data will also be provided as applicable.

For time-to-event variables, the general censoring methods are specified in Section 2.5.3 for fatal or non-fatal time-to-first event endpoints, and in Section 2.6.1 for time-to-recurrent event endpoints.

Some missing or partially missing dates in the analyses require imputation. The handling of missing or partially missing dates has been detailed in Section 5.1.

The randomization in this study will be stratified by region and type of MI (STEMI or NSTEMI). “Other” type of MI has been grouped together with “NSTEMI” as “NSTEMI/Other” type of MI for stratification at randomization. In this document, “NSTEMI” refers to the grouping of “NSTEMI/Other” for type of MI. The stratification factors will be appropriately accounted for in the planned statistical analyses. At Visit 101 all eligible patients will be randomized via Interactive Response Technology (IRT) to one of the treatment arms. The stratification factors of region and type of MI entered and used by IRT at randomization sometimes can be different from the data collected on the Case Report Form (CRF), which is called mis-stratification. In this study, there have been some cases of mis-stratification by type of MI and one case of mis-stratification by region. Analyses using region and/or type of MI will consider the following rules:

- In general, unless otherwise specified, statistical models for all efficacy endpoints will use region and type of MI based on information from IRT where applicable.
- In addition, the primary/main analysis model for each of the primary and secondary efficacy endpoints (Section 2.5 and 2.6) will be repeated using CRF based region and type of MI.

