2.2.1 Subgroups of interest

Subgroups will be formed to explore the consistency of treatment effects and safety profiling on selected parameters between the subgroups and the overall population. In general, subgroups will be defined based on baseline information as defined in [section 2.1](#).

In Table 2-1, we have listed all subgroups defined for this study and the ways to derive them. Subsets of these subgroups will be used depending on the parameter under consideration. Also note that only important parameters or variables in these analyses will have subgroup analyses. The details about the parameters having subgroup analyses will be presented in the corresponding sections as appropriate. Also, additional subgroups may be formed later for regional or country-wise analyses as applicable.

Table 2-1 Specification of subgroups

Subgroup	Method of derivation	Disposition/ Background & Demographics / Exposure	Efficacy	Safety
Number of cardiovascular (CV) risk factors (1 CV risk factor vs. > 1 CV risk factor) ¹	Screening		X	
Age groups: (<65 vs. ≥65 years, <75 vs. ≥75 years)	Screening (derived)	X	X	X
Gender (male/ female)	Screening	X	X	X
Race	Screening	X	X	X
Region*	Derived (pooled countries or country), using Screening	X	X	X
Baseline LVEF (by quartiles)	Screening		X	
Baseline LVEF ≤40% vs. > 40%	Screening		X	
Worst Killip class (I vs. ≥ II)	Randomization		X	
Type of MI (STEMI vs. NSTEMI)		X	X	X
Infarct location (anterior, inferior, and other)			X	
PCI use at baseline (PCI use versus medical management after index MI)	Randomization	X	X	

Subgroup	Method of derivation	Disposition/ Background & Demographics / Exposure	Efficacy	Safety
Time from the index MI presentation to randomization (< median, ≥median)			X	
Baseline SBP (three groups: ≤110 mmHg; >110 mmHg and ≤140 mmHg; >140 mmHg)	Randomization		X	
Screening eGFR (<60 vs ≥ 60 mL/min/1.73 m ²)			X	
History of diabetes (yes/no)	Screening		X	
Atrial Fibrillation associated with index MI at baseline (yes/no)			X	
Prior history of MI			X	
History of hypertension (yes/no)	Screening		X	
Prior ACEi or ARB use (yes/no)			X	
Use of β-blocker at baseline (yes/no)			X	
Use of mineralocorticoid antagonists at baseline (yes/no)	Randomization		X	
Use of loop diuretics at baseline (yes/no)			X	

* **North America:** Canada, USA

¹ Patients with no CV risk factor are categorized in the "1 CV risk factor" group.

Latin America (including Central America): Argentina, Peru, Brazil, Colombia, Mexico

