There are two points to be considered in the sample size re-estimation: the estimated lower event rates and a potentially higher hazard reduction in the primary endpoint. As shown in [Table 3-4](#) and [Table 3-5](#), the estimated event rates using blinded data are lower than the originally assumed event rates, for both the primary endpoint (see [Table 3-4](#)) and the double composite endpoint (see [Table 3-5](#)). An RRR of 19% is assumed for the primary endpoint in place of the original RRR of 18%. This change is based on the newly available efficacy data from the PIONEER-HF (CLCZ696BUS01) study in hospitalized patients with stabilized acute decompensated heart failure, which showed a 46% relative risk reduction (HR 0.54, 95% CI 0.37, 0.79) in patients treated with sacubitril/valsartan for 8 weeks compared to enalapril for an exploratory composite of serious clinical endpoint of death, rehospitalization for heart failure, implantation of a left ventricular assist device, and inclusion on the list of patients eligible for heart transplantation (Velazquez, et al. 2019). The observed risk reduction on the composite endpoint from the PIONEER-HF study was primarily driven by rehospitalization. Given a similar underlined pathophysiological mechanism between HFrEF and post-AMI with left ventricular dysfunction, and also acute setting for both PIONEER-HF and PARADISE-MI studies, this new data indicated that the effect size may have previously been underestimated.

Following the blinded sample size re-estimation, a sample size of 5,650 patients, randomized to LCZ696:ramipril using a 1:1 allocation ratio, has been chosen with the aim to obtain at least 708 first primary endpoint events and at least 592 first CV death or HF hospitalization events in this event-driven study. Seven hundred eight primary endpoint events will provide 80% power assuming a true Relative Risk Reduction (RRR) of 19% (i.e. a hazard ratio of 0.81) for LCZ696 vs ramipril with statistical testing at the overall 2.5% 1-sided type I error rate (with strong control of the FWER). Five hundred ninety two first CV death or HF hospitalization events will provide 77.5% nominal power assuming a true RRR of 20% (for the ITT analysis) for this double composite endpoint for the same type I error rate.

Additional assumptions are described below.

- 0.5% per year lost to follow-up rate (same as the original protocol assumption)

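### The log-rank sensitivity test of the primary endpoint is stratified by MI type only, although randomization was stratified by region as well: a minor improvement that costs almost nothing

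*SAP*

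**What the plan says.** - **Randomization.** Protocol 5.3: "Randomization will be stratified by region and type of index MI (STEMI or NSTEMI" (the closing bracket follows). SAP 2.1 names the same two factors and adds: "The stratification factors will be appropriately accounted for in the planned statistical analyses".
- **Primary analysis.** SAP 2.5.2 specifies a Cox model "stratified by STEMI/NSTEMI, with treatment, PCI use at baseline and region included as factors in the model". MI type is a stratum and region a covariate, so both randomization factors are used.
- **Log-rank test.** Protocol 9.4.4 and SAP 2.5.4 compare the arms "using a stratified log-rank test with STEMI/NSTEMI as a stratification factor". In SAP 2.5.4 this appears twice: item 1(1), for early stopping or termination with events before 01-Mar-2020, and item 2(1), for continuation to the end with all events up to the cut-off. Region appears in neither, and no reason is given. No other log-rank test is listed for the primary endpoint.
- **Other analyses of the primary endpoint.** SAP 2.5.4 includes, in both scenarios, "Analysis with adjustment of country instead of region in the primary analysis model as specified in" SAP 2.5.2. Its during-COVID Cox model and its Weibull model adjust for region. SAP 2.1 also repeats the primary model with CRF-based region and MI type.

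**The concern.** When allocation is balanced within a prognostic factor, the treatment comparison varies less than an analysis ignoring that factor supposes. The test statistic then has a standard deviation a little below 1 and the test is conservative. Leaving a prognostic factor out of a hazard comparison also pulls the estimated effect slightly towards the null. Both effects cost power, and both depend on how far event rates differ between regions.

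The SAP itself expects geography to matter. It justifies the country-adjusted Cox analysis by heterogeneity in COVID-19 impact and in standard of care among countries. Against that background, the one log-rank test drops a randomization factor that the Cox and Weibull models keep. At stake are a little power in a supportive test and one avoidable difference between that test and the Cox analysis it is meant to check.

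**Working it through.** **1. Use of each factor**

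| Factor | Randomization | Primary Cox model | Log-rank test |
|---|---|---|---|
| MI type | stratum | stratum | stratum |
| Region | stratum | covariate | not used |
| PCI use at baseline | not used | covariate | not used |

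The mismatch with SAP 2.1 concerns region. PCI use is a further difference between the two tests, but it was not a randomization factor.

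**2. The plan's own figures.** SAP 3.2 gives 708 events for 80% power at HR 0.81, with one-sided 0.0249 at the final analysis. By Schoenfeld's formula:

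- Events = 4 (z_alpha + z_power)^2 / (ln HR)^2 = 4 x (1.962 + 0.842)^2 / (0.2107)^2 = 708.
- Power at 708 events = Phi(sqrt(708) x 0.2107 / 2 - 1.962) = Phi(0.842) = 80.0%.
- At the current final level of 0.0244 (SAP 2.14), the same single-look formula gives 79.8%.
- The 0.0244 itself also reproduces. With looks at 464, 0.8 x 708 = 566.4 and 708 events, and nominal levels of 0.001 and 0.005 at the interims, a trivariate normal calculation with total alpha 0.025 leaves 0.0244.

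Schoenfeld's formula does not involve strata, so none of these figures moves if region is added.

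**3. Feasibility.** SAP 2.2.1 defines five regions, so there are 2 x 5 = 10 strata. The average is 708 / 10 = about 71 events per stratum at the full target, or 566.4 / 10 = about 57 in the early-stop scenario. Actual counts will be uneven, and the documents do not give them.

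**4. Size of the effect, by paired simulation.** Each simulated trial was tested twice: stratified by MI type only, and by MI type x region.

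*First simulation.* From the plan: N = 5,650, 1:1 allocation, HR 1 or 0.81, one-sided 0.0244. Assumed: blocks of 4; region shares 10/12/33/30/15%; half of patients with each MI type, with hazard multipliers 0.85 and 1.15; exponential event times; uniform censoring from 4 to 34 months, giving about 700 events; a ratio of highest to lowest regional hazard of 1, 2 or 4. There were 1,500 trials per setting.

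| Regional hazard ratio (assumed) | Type I error, MI only | Type I error, MI x region | Power, MI only | Power, MI x region |
|---|---|---|---|---|
| 1 | 2.4% | 2.5% | 80.2% | 80.0% |
| 2 | 2.1% | 2.3% | 78.9% | 79.3% |
| 4 | 1.8% | 1.9% | 80.6% | 81.6% |

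The Monte Carlo standard error of each entry is about 0.4 points for type I error and 1 point for power; pairing makes the within-row differences more precise than that. Rows should not be compared with each other, because event counts varied. The two Z statistics correlate at about 0.997 or higher throughout.

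*Second simulation.* Five regions, two MI types and 3,000 trials per setting, with regional differences set by an assumed between-region SD of the log hazard.

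| Between-region SD (assumed) | Power, MI only | Power, MI x region | Gain from adding region |
|---|---|---|---|
| 0 | 79.2% | 78.9% | -0.3 |
| 0.3 | 80.27% | 80.40% | 0.13 |
| 0.5 | 79.13% | 80.13% | 1.00 |

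With SD 0.3 to 0.5, the standard deviation of the MI-only Z was about 0.98 instead of 1.

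The two simulations agree. Adding region makes no material difference when regions are alike and gains up to about 1 point of power when they differ strongly.

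**The case against.** The strongest reply is that nothing is broken. The SAP 2.1 sentence is a general one and does not promise that every sensitivity test will stratify on both factors; the primary model and those derived from it satisfy it. The log-rank test uses exactly the stratum of the Cox model, without its covariates, and is a coherent, less adjusted companion to it. SAP and protocol agree on it. It carries no alpha and has no place in the hierarchy of SAP 2.6.3, so no decision depends on it. The gain rests on assumed regional differences, and at the fourfold ratio the 10-stratum test was itself at 1.9%.

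Most of this stands, and it is why the point is minor. It does not supply a reason for leaving out a factor by which the trial was randomized, in a plan that adjusts for geography in its other models.

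A reader might also infer that the log-rank test is the only rank-based check. It is not: the Cox partial likelihood also uses only the order of event times, and several Cox analyses of the primary endpoint adjust for region or country. Nor would region strata settle a disagreement between the log-rank and Cox results. With correlations of 0.997 or higher between the two log-rank versions, region would rarely be the cause, and PCI use would still separate log-rank from Cox.

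**Conclusion.** The point holds as a minor improvement. The only log-rank test of the primary endpoint omits one of the two randomization factors without explanation, which sits awkwardly with SAP 2.1. Under assumed regional hazard ratios of 1 to 4, or between-region SDs of 0 to 0.5, the cost is about 0 to 1 point of power in a supportive test, with slight conservatism. With no regional difference there is no material cost.

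Two stronger readings are not supported. The primary result does not ignore region, because SAP 2.5.2 includes it in the Cox model. Type I error is not inflated: the simulated values for the current test were 1.8 to 2.4% against a nominal 2.44%. The 708 events, the 80% power and the 0.0244 all stand.

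**What to change.** In SAP 2.5.4, items 1(1) and 2(1), stratify the log-rank test by MI type x region (10 strata), using the IRT values that SAP 2.1 sets for efficacy models. Protocol 9.4.4 carries the same wording, so either align it or record the change in SAP Section 4, which now reads as not applicable. If the sponsor prefers the present test, a sentence saying why region is left out would be an adequate answer.

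The cost is two short SAP edits, one protocol edit or one Section 4 entry, and an added stratification term in the program, all before database lock. Sample size, boundaries and the primary analysis are untouched. The SAP should not present the revised test as matched to the Cox model, because PCI use remains in one and not in the other, and region is a stratum in one and a covariate in the other.
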